7. STUDY PROCEDURES

As part of the screening and enrollment process, patients with suspected AIS will have either a non-contrast CT head with RAPID calculation of ASPECT score or a CT-perfusion head. Using standard stroke alert treatment protocols at this institution, the RAPID software is used in most potential stroke patients at our institution and will be used to calculate infarct and penumbral volume and targeted diffusion/perfusion mismatch for this study. As part of the screening process, medical charts and EMS reports will be accessed by study personnel as needed to ensure potential subjects meet all inclusion/exclusion criteria. The screening and enrollment procedures along with collection of initial vitals will occur almost simultaneously given the very acute nature of the presentation and desired short interval from ED presentation to randomization. No data will be collected during the screening process that is not part of routine patient care prior to subject enrollment. Routine patient demographics, past medical history, medications, and prehospital assessments will be obtained from chart review. No research data that is not already part of routine patient care will be entered into the subject medical records. Randomization will occur in a 1:1 fashion between the two treatment groups. The estimated study duration is 30 months to allow for full enrollment of subjects and the 3-month mRS assessment. Each subject will be followed for a total of 90 days from enrollment to final assessment. No results from this study will be shared with subjects.

[figure not shown]
Once consented and enrolled in the study, subjects will have the following procedures: (See Table 1 for Schedule of Activities).

1. *Infarct progression:*

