5. *Vital signs* - The determination of need for additional supplemental oxygen in a patient that becomes hypoxic (pulse oximetry<94%) will be determined by the subject's treating physician irrespective of study interventions. Should a patient be found to require additional supplemental oxygen while enrolled in the study, this will be noted and the patient will continue through the final study assessments. The patient's treating physician will also be responsible for routine monitoring and interpretation of other vital signs such as blood pressure and heart rate. If at study assessment time points the study personnel note a subject to have significant vital sign abnormalities (SpO₂<94%, SBP>180mmHg, DBP>110mmHg, SBP<90mmHg, HR>120, HR<50), the study PI and patient's treating physician will be notified to ensure proper documentation. Interventions will be left to the discretion of the patient's treating physician.

Table 1: Schedule of Activities:

Procedures	Baseline/Enrollment ED presentation -T0 (ED arrival +/-60min)	T1 (T0+4hours +/- 20min)	T2 (T0+24hours +/- 4hours)	T3 - Final Assessment (T0+3mo +/- 2weeks)
Informed consent	X			
Demographics	X			
Medical history	X			
Randomization	X			
Administer study intervention		X		
Vital signs: HR, BP, RR, SpO ₂	X	X	X	
ABG		X		
CT-perfusion or CT-head with ASPECTS	X			
Repeat MRI-head (CT-head if unable to get MRI) ^a			X	
Serum sample ^b	X	X	X	
NIHSS	X	X	X	
mRS	X			X
Adverse event review and evaluation		X	X	

^a only routine re-imaging will be obtained
^b tested for selected biomarkers (IL-6, IL-8, and MMP-9)

Assessment of study intervention adherence:

1. Compliance with study interventions will be directly observed at the given time points. If at any observation period a subject is found not to be compliant with the study intervention, medical records will be reviewed to determine the timing of termination of the supplemental oxygen/medical air.
2. All cases of non-compliance with study interventions will be recorded.

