4. Development of respiratory compromise – While patients are continuously assessed by their treating medical team, study personnel will specifically assess study subjects at the T0+4hour and T0+24hour evaluations for worsening respiratory status and the need for additional supplemental oxygen. At the final 3-month assessment, patients' medical records will also be reviewed for evidence of respiratory deterioration while the patient was hospitalized and up to this final assessment including: need for additional supplemental oxygen, need for non-invasive positive pressure ventilation, mechanical ventilation, development of pulmonary edema, development of pneumonia.
5. Development of post-stroke infections – Neuroinflammation after a stroke also results in immunosuppression. As such, this places patients at increased risk of post-stroke infections, the two most common being pneumonia and urinary tract infections which may account for up to 30% of deaths after an AIS⁶⁰. Additionally, there may be sex-based differences in post-stroke infections that could be related to underlying hormone status⁶¹. As such, patients will be screened at the 3-month assessment to determine if they experienced any post-stroke hospitalizations and/or treatment for pneumonia, urinary tract infections, sepsis, or other infections. In addition to asking subjects directly at this assessment, their medical record will also be reviewed for re-admissions while it is being reviewed for the above respiratory compromise.

Definition and Classification of Adverse Events: An adverse event means any untoward medical occurrence, unintended sign, symptom, or disease temporarily associated with the use of an intervention in humans, whether or not considered intervention-related. All AEs will be documented and analyzed further. Subjects will be monitored for signs of an AE at T0+4hr and T0+24hours.

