All AEs including local and systemic reactions not meeting the criteria for SAEs will be captured on the appropriate case report form (CRF). Information to be collected includes event description, time of onset, clinician's assessment of severity, relationship to study intervention (assessed only by those with the training and authority to make a diagnosis), and time of resolution/stabilization of the event. All AEs occurring while on study must be documented appropriately regardless of relationship. All AEs will be followed to adequate resolution.

Any medical condition that is present at the time that the participant is screened will be considered as medical history and not reported as an AE. However, if the study participant's condition deteriorates at any time during the study, it will be recorded as an AE.

Changes in the severity of an AE will be documented to allow an assessment of the duration of the event at each level of severity to be performed. AEs characterized as intermittent require documentation of onset and duration of each episode.

The study PI will record all reportable events into a database with start dates occurring any time after randomization until completion of the study. At T0+24hours, study personnel will inquire about the occurrence of AE/SAEs since the last observation point. Solicited and unsolicited events will be captured. Unsolicited AEs will be identified by asking participants if they "have noticed anything different since beginning the treatment after the onset of your stroke." Solicited AEs will include: 1) any trouble breathing, 2) development of pneumonia, 3) need for additional oxygen therapy, 4) hemorrhagic conversion of the stroke. Events will be followed for outcome information until resolution or study completion.

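### Adverse events are to be documented throughout the study, but open AE/SAE review is scheduled only at 4 and 24 hours, so some later events would be under-ascertained

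*Combined protocol and SAP*

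**What the plan says.** **What must be recorded.** Section 16 says "All AEs occurring while on study must be documented appropriately regardless of relationship". It also has the principal investigator enter reportable events in a database, "with start dates occurring any time after randomization until completion of the study". The term reportable is not defined. Section 7 gives the length of follow-up: "Each subject will be followed for a total of 90 days from enrollment to final assessment".

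**When someone asks.** Section 16 says "Subjects will be monitored for signs of an AE at T0+4hr and T0+24hours" and "At T0+24hours, study personnel will inquire about the occurrence of AE/SAEs since the last observation point". In Table 1 (Section 7) the row "Adverse event review and evaluation" is marked at T1 (4 hours) and T2 (24 hours, window ±4 hours). It is blank at T3 (3 months).

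**What the 3-month assessment covers.** Under Section 16, charts are reviewed for respiratory deterioration. Subjects are screened for "any post-stroke hospitalizations and/or treatment for pneumonia, urinary tract infections, sepsis, or other infections", and the chart is checked for re-admissions.

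**What is analysed.** Section 16 says "All AEs will be documented and analyzed further" and gives no method. The Safety Monitoring Committee sees safety data for each arm at least twice a year. Section 17 covers time to randomization and treatment, infarct growth or penumbral salvage, NIHSS, average 3-month mRS and biomarkers. It states no summary of adverse events or deaths by arm.

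**The concern.** The duty to record runs to the end of the study, but the last scheduled open question is put at 24 hours. A site that follows Table 1 exactly can comply with the schedule and still fall short of the documentation rule.

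The loss would not be random across event types. Respiratory and infectious events are actively sought at 3 months; other kinds are not, unless they led to re-admission. An adverse event table built this way would mix actively sought and incidentally noted events, and low counts of the latter could be read as absence of harm.

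This matters because Section 4 names preliminary data on adverse effects as a purpose, alongside feasibility. Sections 2 and 8 also cite an earlier hyperoxia trial that was stopped for safety concerns.

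Death raises a smaller, separate issue. It should be known at 3 months as mRS 6, but the stated analysis folds it into a mean labelled exploratory.

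**Working it through.** **Step 1. Set recording against inquiry.** The plan gives no figure to reproduce here, so the check is a comparison of texts.

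| Period | Recording duty (Section 16) | Scheduled inquiry |
|---|---|---|
| Randomization to 24 h | All AEs | General review at T1 and T2; solicited and unsolicited AEs at T2 |
| 24 h to 3 months | All AEs | Look-back at T3 for respiratory deterioration, infections, hospitalizations and re-admissions |

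The 90-day endpoint is inferred from Section 7, because completion of the study is not defined per subject. The table reading does not depend on how the PDF was extracted: the text of Section 16 gives the same two time points.

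**Step 2. Find what remains uncovered.** I read the 3-month hospitalization question broadly, as any hospitalization after the stroke and not only one for infection. On that reading an event causing re-admission is found. Four conditions together define the gap: onset after 24 hours, not respiratory, not infectious, and either within the index stay or managed without re-admission. A cardiac event on day 3 in hospital, a recurrent stroke during the index stay and a non-cerebral bleed treated as an outpatient all qualify.

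**Step 3. Look for another scheduled route.** Section 16 has personnel and the treating physician monitor regularly, reports any hemorrhagic conversion as an AE, says events may come to light at observation time points or through a study monitor, and counts later deterioration of an existing condition as an AE. None of these sets an inquiry at a stated time after T2.

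**Step 4. Precision of a by-arm death summary.** Inputs: 200 subjects, about 100 per arm (Section 4.1), and 29% loss to follow-up (Section 17, stated there for 24-hour NIHSS and borrowed here). Mortality of 10 to 20%, equal in both arms, is my assumption.

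Half-width of the 95% CI for the risk difference = 1.96 × √(2p(1−p)/n). At 29% loss, n = 100 × 0.71 = 71.

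| n per arm | p = 0.10 | p = 0.20 |
|---|---|---|
| 100 | 1.96 × √(0.18/100) = 8.3 points | 1.96 × √(0.32/100) = 11.1 points |
| 71 | 1.96 × √(0.18/71) = 9.9 points | 1.96 × √(0.32/71) = 13.2 points |

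These widths allow description only.

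**Step 5. Context from the cited trial.** Section 8 gives deaths judged unrelated to therapy as 16/43 = 37.2% with hyperoxia and 6/41 = 14.6% with normoxia. The difference is 22.6 points (Fisher exact p = 0.025). It shows why deaths deserve their own line; it does not measure the size of the present gap.

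**The case against.** The strongest reply is that the process exists and only a tick in Table 1 is missing. Monitoring by staff and the treating physician has no end date in Section 16, T3 is itself an observation time point, and the 3-month review looks back over the whole period for the events most plausibly linked to oxygen. Treatment lasts only 4 hours, so an early focus is partly a design choice. Much of this stands, and it narrows the gap to the events in Step 2. It does not close it, because unscheduled routes depend on someone happening to notice and report.

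On death, the reply is stronger still. Death is a criterion for a serious event, it is mRS category 6, and safety data by arm reach the Safety Monitoring Committee. The study is not powered for secondary outcomes. What is missing is only a pre-stated summary.

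A reader might infer more than the documents support:

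- **That no safety data are collected after 24 hours, or that only about 1% of follow-up is covered.** One day in 90 locates the last general review. It ignores the look-back at T3.
- **That deaths will be missed, or that the mean mRS will hide an excess.** Deaths should be known when vital status is obtained. Whether a mean would hide a difference depends on mortality and survivor distributions that the documents do not give. A table of mRS 0 to 6 by arm would also show deaths.
- **That the cited trial shows brief hyperoxia raises mortality.** It used 45 L/min, the deaths counted were judged unrelated, and cardiac disorders were similar (4/43 against 5/41).

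**Conclusion.** The point holds in a limited form. Section 16 requires documentation of all adverse events on study, while Table 1 and the time points in Section 16 provide open review only to 24 hours (28 hours at the edge of the T2 window). The targeted 3-month check leaves non-respiratory, non-infectious events unsought when they arise after 24 hours in the index stay or without re-admission. If the schedule is followed as written, these would be under-ascertained. How many would be lost cannot be estimated, since the documents give no rates for them. The conclusion rests on taking 90 days as each subject's study period and on the broad reading of the hospitalization question; a narrower reading would widen the gap.

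The primary feasibility endpoint is unaffected; the stated aim of gathering preliminary adverse-effect data is weakened. The absence of a by-arm death summary from Section 17 is a secondary omission in reporting, not a failure to capture deaths.

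**What to change.** 1. Reconcile Table 1 and the monitoring times in Section 16 with the documentation rule. Mark adverse event review at T3, and say that the 3-month call and chart review cover all AEs and SAEs since T2, with the open question used at 24 hours asked again. Define reportable, and state when a subject's recording period ends.
2. Add one descriptive line to Section 17: 90-day all-cause deaths by randomised arm, as counts and a risk difference with 95% CI, with the number whose vital status is unknown.

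The cost is one mark in Table 1, a few sentences of text and one line of results, with no new visit and no change in sample size. The downside is a slightly longer 3-month call and chart review, and more late events unrelated to treatment to record.

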An adverse event (AE) or suspected adverse reaction is considered "serious" if it results in any of the following outcomes: death, a life-threatening adverse event, prolongation of existing hospitalization, a persistent or significant incapacity or substantial disruption of the ability to conduct normal life functions. Important medical events that may not result in death, be life-threatening, or require hospitalization may be considered serious when, based upon appropriate medical judgment, they may jeopardize the participant and may require medical or surgical intervention to prevent one of the outcomes listed in this definition.

For adverse events (AEs), the following guidelines will be used to describe severity.

- **Mild** – Events require minimal or no treatment and do not interfere with the participant's daily activities.
- **Moderate** – Events result in a low level of inconvenience or concern with the therapeutic measures. Moderate events may cause some interference with functioning and/or the need for further supplemental oxygen or antibiotic treatment.
- **Severe** – Events interrupt a participant's usual daily activity and may require systemic drug therapy or other treatment. Severe events may include need for mechanical ventilation, vasoactive infusion, are usually considered potentially life-threatening or incapacitating.

The PI will be responsible for determining whether an adverse event (AE) is expected or unexpected. An AE will be considered unexpected if the nature, severity, or frequency of the event is not consistent with the risk information previously described for the study intervention.

The following AEs are considered to be expected:

1. Bleeding and/or hematoma formation at sight of arterial puncture
2. Pain at the sight of arterial puncture lasting after collection of ABG
3. Hemorrhagic conversion in up to ~40% of study subjects

The occurrence of an adverse event (AE) or serious adverse event (SAE) may come to the attention of study personnel during study observation time points or upon review by a study monitor.

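### The definition of a serious adverse event counts a prolonged stay but not a new admission, so an adverse event that leads to readmission is not automatically serious

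*Combined protocol and SAP*

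**What the plan says.** All of this is in Section 16 (Data and Safety Monitoring Plan), except where noted.

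- **Seriousness list.** An adverse event is serious if it results in "death, a life-threatening adverse event, prolongation of existing hospitalization, a persistent or significant incapacity", or in substantial disruption of normal life functions. Prolongation is the only item that concerns hospital care.
- **Important medical events.** The next sentence reads: "Important medical events that may not result in death, be life-threatening, or require hospitalization may be considered serious when, based upon appropriate medical judgment". The conditions it attaches are risk to the participant and a possible need for intervention to avert a listed outcome.
- **3-month screen.** Under post-stroke infections, "patients will be screened at the 3-month assessment to determine if they experienced any post-stroke hospitalizations" or treatment for infection, and "their medical record will also be reviewed for re-admissions". The respiratory item adds a record review up to the final assessment.
- **Recording window.** Reportable events are entered "with start dates occurring any time after randomization until completion of the study".
- **Scheduled review.** "Subjects will be monitored for signs of an AE at T0+4hr and T0+24hours". Table 1 in Section 7 agrees: adverse event review is marked at T1 and T2, not at T3.

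**The concern.** The important-medical-event sentence is a catch-all for events that miss the main criteria. It names death, threat to life and need for hospitalization as those criteria. The first two are on the list. The third is there only as prolongation of a stay already under way. The intended rule and the stated rule therefore differ, and it is the stated rule that assessors would apply.

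What is at stake is the consistency of the safety data. The Safety Monitoring Committee is to review safety by arm at least twice a year, and its membership includes investigators (Section 16). Section 4 concedes that full blinding cannot be guaranteed. Two sites enroll (Section 3). Section 16 gives the decision on expectedness to the principal investigator but names no one to decide seriousness. The background also reports an earlier hyperoxia trial that was stopped early over safety. In that setting, seriousness should rest on a fixed rule as far as possible and not on case-by-case judgment.

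**Working it through.** No arithmetic applies. The check sets the clauses side by side and applies them to cases.

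**Step 1: is new admission covered anywhere?** The seriousness list does not contain it. The severity scale, the recording rules, the withdrawal section, Table 1 and the analysis plan add no seriousness criterion. The sentence holding the list is complete, so neither redaction nor a broken table explains the gap.

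**Step 2: does the catch-all fill the gap?** Only in part. It is permissive and depends on medical judgment. It is also tied to preventing one of the listed outcomes, and new admission is not one of them.

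**Step 3: apply the rule as written.**

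| Case | Serious on the ground of hospital care? | Other route to serious |
|---|---|---|
| Pneumonia that prolongs the index stay | Yes, automatically | Not needed |
| The same pneumonia, after discharge, causing a new admission | No | Another listed criterion, or judgment |
| Readmission with a fatal, life-threatening or incapacitating event | No | Yes, by another listed criterion |
| Planned or elective readmission with no untoward event | No | None; not an adverse event |

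The first two rows show the anomaly: the same illness is treated differently according to whether the patient had already gone home. The severity scale makes the second row easy to under-classify, because it gives a need for antibiotics or further oxygen as an example of a moderate event.

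**Step 4: will such cases arise in the data?** The trial expects to find them. The 3-month interview and record review look for hospitalizations and readmissions, including those for pneumonia, urinary tract infection and sepsis, and the recording window runs to study completion. Readmissions by 3 months are therefore actively sought and inside the window, but have no seriousness status of their own.

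**Step 5: how do they reach the safety record?** Adverse event review is scheduled at 4 and 24 hours only. The documents do not say how a readmission found at 3 months is carried into the adverse event record and classified.

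**The case against.** The strongest reply is that little is lost. Section 16 requires all adverse events to be documented, with severity and whatever their relationship to treatment, and the 3-month review seeks readmissions in any case. A readmission can still be serious as life-threatening, as an incapacity, arguably as a substantial disruption of normal life, or by medical judgment. The catch-all sentence shows what the authors meant, so this looks like a dropped phrase and not two competing rules. Section 17 plans no comparison of serious events, and no stopping rule depends on them. The same definition applies to both arms.

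Most of that stands, and it limits the point. A reader might infer that readmissions cannot be serious or will go unrecorded; the documents support neither. A reader might also infer that the omission favours one arm. Nothing shows that: a common definition applied evenly does not tilt the comparison, and the remaining risk is uneven judgment. Nor do the documents support calling readmission a likely form of delayed harm from a 4-hour exposure; Sections 2 and 8 argue that the short exposure minimizes the lung risk.

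The reply does not remove the inconsistency. A visible intention is not a rule, and the substantial-disruption and judgment routes are the ones on which assessors can differ.

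**Conclusion.** Wrong as written. The list omits new inpatient hospitalization, while the sentence after it presupposes that criterion. The consequence is that an adverse event leading to readmission is not automatically serious on the ground of admission, so counts of serious events by arm could be too low and inconsistent between assessors and sites.

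The size cannot be derived from the documents. A reader might assume a 90-day readmission rate of, say, 10–20% and get 0.10 × 200 = 20 to 0.20 × 200 = 40 subjects. The documents give no such rate. Even if it were right, the figure would count every readmission, including those already serious on other grounds and those that are not adverse events. It would be at most an upper bound under that assumption, and the finding does not rest on it.

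The conclusion rests on the text alone, on the assumption that the seriousness list is meant to be exhaustive apart from the important-medical-event clause. The point concerns classification, not whether the events are looked for.

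**What to change.** 1. In the seriousness list in Section 16, insert *inpatient hospitalization or* immediately before the prolongation item. The list then agrees with the important-medical-event sentence.
2. State that a readmission found at the 3-month interview or record review, if it results from an adverse event, is entered in the adverse event record and classified under the amended definition. Planned or elective admissions without an untoward event are excluded. Coding every readmission as serious would go too far.

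The first change is three words. The second needs a short line of procedure for the 3-month assessment, using information already being collected. Neither alters treatment, visits or endpoints. The downside is a somewhat higher count of serious events and a little more reporting work.

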8. RISKS TO SUBJECTS

Hyperoxia has been explored in various disease states. While meta-analysis in myocardial infarction did not show an increase in mortality, hyperoxia has been shown to have negative cardiovascular and hemodynamic effects in cardiac patients. In some, but not all cardiac disease states, there were decreases in heart rate and cardiac output and increases in systemic vascular resistance⁴⁰. These potential decreases in cardiac output and increases in

systemic vascular resistance could negatively impact stroke patients, especially those with perfusion dependent lesions.

The most commonly proposed potential harm from hyperoxia therapy is the increased production of reactive oxygen and nitrogen species that not only may contribute to reperfusion injury, but may also lead to hyperoxic lung injury. Rodent MCAO models suggest that this risk is low given there was no evidence of such effects when therapy was instituted immediately after the ischemic event¹⁴⁻¹⁹. This issue has also been evaluated in rodent models and in human models in critically ill patients. In an endotoxemia model (induced by the administration of lipopolysaccharide derived from E.coli), brief hyperoxia with a PaO₂ of ~400mmHg for 3.5 hours in humans resulted in no change in the ability to mount a cytokine and inflammatory response⁴⁴. Both hyperoxic and control subjects had similar patterns of expression of tumor necrosis factor alpha (TNF- α), interleukin-6 (IL-6), IL-8, or IL-10 in response to endotoxemia. Additionally, hyperoxia treatment did not clinically alter the leukocyte population produced in response to endotoxemia, nor the ability for neutrophils to undergo phagocytosis. Hyperoxic lung injury has been demonstrated in patients exposed to hyperoxia for long periods of time but has not been evaluated in those with brief hyperoxia exposures^{45,46}. Thus, by limiting the oxygen therapy in this clinical trial to no more than 4 hours, the study will minimize this potential risk.

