Further safety concerns regarding possible increased mortality resulting from hyperoxia therapy were also raised with a multicenter retrospective study that determined the 28-day mortality in all mechanically ventilated intensive care unit (ICU) stroke patients (including ischemic stroke, subarachnoid hemorrhage (SAH), and intracerebral hemorrhage (ICH)). This study found an increased mortality in all stroke patients found to be hyperoxic (defined as a 24-hour post-admission PaO₂ >300mmHg)⁴⁷. However, upon subgroup analysis, increased mortality was only seen in the hyperoxic SAH and ICH groups compared to normoxic controls, and there was no significant difference in mortality in the AIS patients exposed to hyperoxia (43% in-hospital death at 28 day in normoxic patients vs 57% in hyperoxic patients, p=0.13)⁴⁷. This was further supported by a second study of ICU stroke patients being mechanically ventilated that failed to demonstrate an association between oxygenation level (PaO₂) and mortality⁴⁸. The safety of hyperoxia in AIS patient was also questioned in a recent unpublished clinical trial (NCT00414726) studying hyperoxia, that randomized patients to room air or 45L/min via facemask. The trial was terminated early, after enrolling only 85 participants, for safety concerns⁴⁹. However, upon closer blinded review of the results, only one death in each group was determined to be possibly related to the therapy. The remainder (16/43 deaths in the hyperoxia group, 6/41 deaths in normoxia group) were determined to be unrelated to therapy. However, the exact cause of death was not reported. Additionally, there similar rates of cardiac disorders between the hyperoxia vs normoxia groups (4/43 vs 5/41) and pulmonary related adverse events (3/43 vs 2/41). As such, a similarly designed clinical study in Europe began recently. Taken together, the data suggests that the safety of hyperoxia therapy is disease-specific and short exposures to hyperoxia in AIS patients is safe. However, the exact immediate and long-term effects of brief hyperoxia in AIS are not fully understood.

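### Cardiac events are named in neither the solicited adverse-event list nor the 3-month record review, so they are likely to be under-counted, mainly after 24 hours

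*Combined protocol and SAP*

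**What the plan says.** Section 8 begins its account of harm by saying that "hyperoxia has been shown to have negative cardiovascular and hemodynamic effects in cardiac patients". It describes changes in heart rate, cardiac output and systemic vascular resistance, and adds that the last two could be detrimental in stroke, particularly where lesions depend on perfusion. Later in the section it reports cardiac disorders in 4/43 hyperoxia and 5/41 normoxia patients of a stopped stroke trial, calls the rates similar, and uses them in the argument that brief exposure is safe.

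Section 16 lists what will be asked about: "Solicited AEs will include: 1) any trouble breathing, 2) development of pneumonia, 3) need for additional oxygen therapy", and, as the fourth and last item, hemorrhagic conversion. At 3 months, "medical records will also be reviewed for evidence of respiratory deterioration while the patient was hospitalized and up to this final assessment". Besides additional oxygen, the items to look for are "need for non-invasive positive pressure ventilation, mechanical ventilation, development of pulmonary edema, development of pneumonia". Under post-stroke infections, subjects are screened for "any post-stroke hospitalizations and/or treatment for pneumonia, urinary tract infections, sepsis, or other infections", and "their medical record will also be reviewed for re-admissions while it is being reviewed for the above respiratory compromise".

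Section 16 also contains general rules. All on-study adverse events are to be documented whatever their relationship to treatment. The investigator records reportable events from randomization to study completion. Participants are asked an open question about anything they have noticed. The definition of a serious event is generic. Active adverse-event monitoring is set at 4 and 24 hours, and Table 1 in Section 7 schedules adverse-event review at T1 and T2 but not at T3.

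**The concern.** The plan looks systematically for lung, infection and bleeding events, but not for clinical cardiac events, although cardiovascular effects are the first harm it discusses and cardiac disorders are a category it cites by arm as reassurance.

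The population makes this relevant. Section 2 reports reduced cardiac output under hyperoxia in patients with coronary artery disease and heart failure. Exclusion criterion 8 removes only patients being treated for acute myocardial infarction or decompensated heart failure at presentation, so patients with stable coronary disease or chronic heart failure can enroll.

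Section 4 says the trial is to gather preliminary data on adverse effects. The Safety Monitoring Committee is to review safety data by arm at least twice a year. A category that is not actively sought is likely to reach both uses incomplete.

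**Working it through.** The plan states no figure on this point, so the main check sets the text side by side. The arithmetic is for scale only.

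**1. Named items.**
- Solicited list: trouble breathing, pneumonia, additional oxygen, hemorrhagic conversion. Cardiac items: 0 of 4.
- 3-month respiratory review: additional oxygen, non-invasive ventilation, mechanical ventilation, pulmonary edema, pneumonia. Only pulmonary edema could be cardiac in origin, and it is filed as respiratory.
- 3-month infection screen: hospitalizations, infection treatment, re-admissions. No cardiac diagnosis is named.

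**2. How a cardiac event could reach the data, by when it occurs.**
- *Up to 24 hours:* adverse-event review at T1 and T2, the open question, heart rate and blood pressure with alert limits, and the treating team. Several routes exist, but none asks about cardiac events by name.
- *After 24 hours, still in the index stay:* general recording, and the serious-event definition if the event is fatal, life-threatening or prolongs the stay. The 3-month chart review covers this period but is directed at respiratory deterioration.
- *After discharge, with re-admission:* the re-admission review should show it, although that text sits under infections.
- *After discharge, without re-admission:* passive reporting only.

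The weak cells are the second and the fourth.

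**3. How much reassurance the cited counts give.** Inputs are from Section 8.
- p1 = 4/43 = 9.30%; p2 = 5/41 = 12.20%; d = p1 − p2 = −2.89 points.
- Wilson 95% limits: 3.68% to 21.60% for p1, and 5.32% to 25.54% for p2.
- Newcombe lower limit: d − √[(p1 − l1)² + (u2 − p2)²] = −2.89 − √(5.63² + 13.35²) = −2.89 − 14.49 = −17.4 points.
- Newcombe upper limit: d + √[(u1 − p1)² + (p2 − l2)²] = −2.89 + √(12.30² + 6.87²) = −2.89 + 14.09 = +11.2 points.

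The interval runs from 17 points fewer to 11 points more with hyperoxia. It neither shows an excess nor excludes a material one.

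**4. Scale in this trial.** Assumption: the stopped trial's rates carry over to this population.
- Expected events with 100 per arm: 100 × 9.3% ≈ 9 to 100 × 12.2% ≈ 12.
- Half-width of the 95% CI for the difference, with equal true rates and full capture: 1.96 × √[2p(1 − p)/100]. This is 8.1 points at p = 9.3% and 9.1 points at p = 12.2%.
- If a share c of events were captured equally in both arms, the counts and the observed difference would both be multiplied by c. The documents give no basis for a value of c, so none is assumed.

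**The case against.** The strongest case on the other side has four parts.

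- **The first harm in Section 8 is hemodynamic, and part of it is monitored.** Heart rate and blood pressure are taken at baseline, T1 and T2, with limits that trigger notification. This stands. A cardiac-event line would not measure cardiac output or vascular resistance either. But spot vital signs are not cardiac diagnoses, and they stop at 24 hours. Separately, the upper systolic alert limit is 180 mmHg in Section 7 and 200 mmHg in Section 16, and these passages must be reconciled.
- **General capture exists.** This also stands. A reader might infer that cardiac events can be recorded only if volunteered at 4 or 24 hours, or that the trial cannot count them at all. The documents do not support either reading: recording runs to study completion, serious events are covered by definition, and re-admissions are reviewed. What remains is that a duty to record is not a method of search. The open question also relies on patients whose stroke may impair them, as Section 4.1 acknowledges when discussing capacity.
- **The plan follows its own priorities.** Section 8 calls reactive species, with reperfusion and lung injury, the most commonly proposed harm, and the respiratory items and biomarkers fit that. A reader might infer from the order of discussion that the protocol ranks cardiac harm as mattering most. It does not say so.
- **This is a feasibility study.** Section 17 says it is not powered for secondary or exploratory outcomes. That rules out an argument from lost power, which would rest on assumed rates and capture fractions. It does not remove the value of a complete count.

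A reader might also infer that comparison with the stopped trial becomes impossible. No such comparison is planned, and the documents do not say how that trial ascertained cardiac disorders.

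**Conclusion.** The point holds as a gap in systematic ascertainment. Cardiac events are not named in the solicited list or the 3-month review, although cardiovascular effects come first in Section 8 and cardiac counts form part of its safety argument. The consequence is likely under-counting, concentrated in events after 24 hours in the index stay and events that do not lead to re-admission.

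The size of the under-count cannot be derived from the documents. The figure of 9 to 12 expected events per arm rests entirely on carrying over the stopped trial's rates and shows only the order of magnitude. This is a cheap improvement to a trial meant to supply preliminary adverse-effect data. It is not a flaw that undermines the primary feasibility endpoint.

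**What to change.** Three changes, all to data collection and reporting:

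- Add a fifth solicited item at T1 and T2: cardiac event (myocardial infarction, arrhythmia, heart failure).
- Add the same item to the 3-month record review, covering the index stay after 24 hours as well as the period after discharge.
- State in Section 17 that cardiac events will be tabulated by arm with the difference in proportions and its 95% CI, described as preliminary and not powered. Section 17 currently describes no tabulation of adverse events.

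The cost is one case-report-form item and a short additional look in a chart that is already being opened at 3 months. The downside is slightly more adverse-event data entry.
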